APPENDIX VII: REVISION HISTORY

This CIP may be amended as appropriate by the Sponsor. Rationale will be included with each amended version in the revision history table below. The version number and date of amendments will be documented.

IRB/EC and relevant Regulatory Authorities, if applicable, will be notified of amendments to the CIP.

Clinical Investigation Plan

Clinical Investigation Plan

APPENDIX VIII: CIP SUMMARY

Clinical Investigation Name and Number	ARIES HM3 CRD_971
Title	Antiplatelet Removal and Hemocompatibility EventS with the HeartMate 3 Pump
Background	Heart failure (HF) is a growing epidemic, with 915,000 new cases diagnosed each year, resulting in over 1 million hospitalizations and costs the United States (US) healthcare system over \$30 billion annually ¹ . Left ventricular assist devices (LVAD) are increasingly being used for treating patients with advanced heart failure as they have demonstrated improved survival over optimal medical management ² . Progressively improving outcomes with newer LVAD technology has led to LVAD therapy becoming a mainstay in the treatment of advanced heart failure ³ , however, LVAD therapy has been beleaguered by hemocompatibility related adverse events – namely thrombosis, stroke and bleeding ⁴ . Within the prospective randomized multicenter MOMENTUM 3 clinical trial, the HeartMate 3 (HM3) Left Ventricular Assist System (LVAS; Abbott, Chicago, IL, Study Sponsor) showed a decrease in hemocompatibility related adverse events relative to the HeartMate II (HMII) LVAS (Abbott, Chicago, IL) ⁵ . This included decreases in pump thrombosis ⁶ , stroke ⁷⁻⁹ , and bleeding ⁹ event rates. Despite these noted improvements a high residual risk of bleeding persists in patients treated with the HM3 LVAD ⁹ . Patients implanted with the HM3 pump are treated with a combination of antiplatelet and anticoagulation therapy but the role and implications of this regimen in determining the burden of hemocompatibility related adverse events have not been adequately investigated ^{9,10} . Whether antiplatelet therapy is essential in concert with anticoagulation in treating such patients remains unknown.
Objective	To study the safety and efficacy of an anti-platelet-free antithrombotic regimen in patients with advanced heart failure treated with the HM 3 LVAS
Hypothesis	Withdrawal of aspirin from the antithrombotic regimen of HM3 pump patients will not adversely affect safety and efficacy and may reduce non-surgical bleeding
Clinical Investigation Design	Prospective, randomized, double-blinded, placebo-controlled clinical investigation of advanced heart failure patients treated with the HM3 with two different antithrombotic regimens: vitamin K antagonist with aspirin versus vitamin K antagonist with placebo

Clinical Investigation Plan

Device Under Investigation and Indications	
HeartMate 3 Left Ventricular Assist System (LVAS)
 
In the US, the HM3 LVAS is indicated for providing mechanical circulatory support in patients with advanced refractory left ventricular heart failure (e.g. pending cardiac transplantation or myocardial recovery, or for permanent support). In Europe, the HM3 LVAS is intended to provide long term hemodynamic support in patients with advanced, refractory left ventricular heart failure. It is intended either for temporary support, such as a bridge to cardiac transplantation (BTT), or as permanent destination therapy (DT) and it is intended for use inside or outside the hospital. In Canada, The HM3 LVAS is indicated for providing mechanical circulatory support in patients with advanced refractory left ventricular heart failure (e.g., pending cardiac transplantation or myocardial recovery, or for permanent support).

Treatment Arm Medication	
Aspirin (100 mg— active ingredient: Acetylsalicylic acid) OR Placebo (ALMAC Group, Craigavon, UK)

Study Sites	
Up to 50 US and international sites

Patient Protection Procedures	
This study will employ an independent clinical events committee (CEC), which will remain blinded to subject randomization, to adjudicate primary endpoint related adverse events. Study monitoring will be performed by an independent data safety monitoring board (DSMB), which will be unblinded to population randomization and determine independent rules for safety oversight.

Primary Endpoint	
Composite of Survival free of any non-surgical¹ major hemocompatibility related adverse event² at 1-year post implant.
 
¹Non-surgical – any event occurring > 14-days post implant
 
²Major Hemocompatibility Related Adverse Event:
 
 • Stroke • Pump Thrombosis (suspected or confirmed) • Bleeding (including intracranial bleeds that do not meet the stroke definition) • Arterial Peripheral Thromboembolism

Clinical Investigation Plan

Primary Endpoint Evaluation	The primary endpoint composite success rate will be calculated for each treatment arm based on the number of subjects who survive to 12 months with no primary endpoint events divided by the total number of subjects in the Modified Intention to Treat Population (mITT) population. The placebo arm will be considered non-inferior to the aspirin arm if the lower boundary of the one-sided 97.5% confidence limit of the risk difference in the composite success between treatment arms (Placebo-arm minus Aspirin-arm) is greater than the non-inferiority margin (10%).
Number of Subjects Required for Inclusion in Clinical Investigation	[REDACTED]
Secondary Endpoint	
• Non-surgical Major Hemorrhagic Events• Non-surgical Major Thrombotic Events• Survival• Stroke Rates,• Pump Thrombosis Rates• Bleeding Rates, including:
○ Non-surgical Bleeding○ Moderate Bleeding○ Severe Bleeding○ Fatal Bleeding○ GI Bleeding
Descriptive Endpoints	Hemocompatibility Score, Rehospitalizations, Economic Cost Implications

Clinical Investigation Plan

Subject Follow-up	
- Baseline- Implant- Randomization- Discharge- Week 1 ± 3 days- Month 1 ± 7 days- Month 3 ± 30 days- Month 6 ± 30 days- Month 9 ± 30 days- Month 12 ± 30 days- Every 6 month ± 60 days until last subject has completed the 12-month follow-up.
Inclusion Criteria	
• Subject will receive the HeartMate 3 per standard of care (SOC) in accordance with the approved indications for use in the country of implant.• Subject will receive the HeartMate 3 as their first durable VAD.• Subject must provide written informed consent prior to any clinical investigation related procedure.• In patients of child bearing capability, not currently pregnant and on appropriate contraception.
Exclusion Criteria	
• Post-implant additional temporary or permanent mechanical circulatory support (MCS) post-implant (other than the HM3 LVAD).• Post-implant Investigator mandated antiplatelet therapy for other conditions (including mandated presence or absence of antiplatelet agent).• Patients who are nil per os (NPO) post-implant through day 7.• Subjects with a known allergy to acetylsalicylic acid.• Participation in any other clinical investigation(s) involving an MCS device, or interventional investigation(s) likely to confound study results or affect study outcome.• Presence of other anatomic or comorbid conditions, or other medical, social, or psychological conditions that, in the investigator's opinion, could limit the subject's ability to participate in the clinical investigation or to comply with follow-up requirements, or impact the scientific soundness of the clinical investigation results.

Clinical Investigation Plan

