3.0 CLINICAL INVESTIGATION DESIGN

This is a prospective, randomized, double-blinded, placebo-controlled clinical investigation of advanced heart failure patients treated with the HM3 with two different antithrombotic regimens: vitamin K antagonist with aspirin versus vitamin K antagonist with placebo. Subjects will be randomized in a 1:1 ratio.

Clinical Investigation Plan

The clinical investigation has been designed to involve as little pain, discomfort, fear, and any other foreseeable risk as possible for subjects. Refer to the Risks Analysis section of the clinical investigation plan for details.

The clinical investigation will be conducted at up to 50 centers worldwide. Greater than 50% of the patients enrolled in this study will be from centers based in the United States. The primary and secondary endpoints will be evaluated according to the statistical section (Section 8 and in the study statistical analysis plan; SAP). Outcomes for this study include death, transplant, withdrawal or pump exchange. All subjects, site, Clinical Events Committee (CEC), and sponsor personnel will remain blinded to the randomization scheme until the last ongoing study subject completes follow-up (specifically, experiences an outcome or has final study visit) and all data have been collected and adjudicated. Exceptions will be justified in the study blinding plan (e.g. DSMB). After a patient reaches 12-months of follow up, they will continue to be followed every 6-months, as long as they remain on the treatment arm medication, until the last ongoing patient reaches 12-months of follow up. Beginning at the 12-month follow-up visit, patients should be requisitioned two bottles of the treatment arm medication to cover the 6 months until the next follow up visit.

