5.7 Number of Subjects

This study will enroll enough subjects to randomize 628 subjects in the clinical investigation. No site may randomize more than 15% of the total number of randomized subjects without Sponsor authorization.

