6.4 Baseline

The baseline assessments in table 3 will be performed.

Table 3 – Baseline Data Collection

Study Activity	Data Collection
Informed Consent	Informed consent details
Inclusion/Exclusion	Subject's eligibility details
Demographics	Age, height, gender, ethnicity (except where prohibited by regulation), race (except where prohibited by regulation), blood type, INTERMACS profile, and NYHA class
General and Cardiac Medical History	Etiology of HF, duration of HF, therapeutic intent (BTT/BTC/DT), arrhythmias, prosthetic valve(s), history of stroke, diabetes, smoking, history of bleeding (diverticular disease, diagnosed arteriovenous malformations (AVMs), GI ulcer(s), anemia and/or erythropoietin treatment), aortic stenosis, hypertension, history of MI, peripheral thromboembolism, coronary stents, CABG, substance abuse (drug/alcohol), drug/radiation toxicity, peripheral vascular disease, carotid artery disease, cardiac rhythm management device, intra-aortic balloon pump, other pre-implant circulatory support, CardioMEMS, and HIV status
Modified Rankin Score	Modified Rankin Score (MRS)
Vital Signs	Weight, blood pressure, and heart rate
Anticoagulation/Antiplatelet Medications	Vitamin K antagonist (e.g. warfarin, fluindione, phenprocoumon, etc.), clopidogrel, dipyridamole, other anticoagulation agents, other vitamin K antagonists, direct thrombin inhibitors, etc. (including treatment arm medication) All new medications started, or current medications stopped during the follow-up period must be recorded. All dose changes (including IV titrations as total daily dose) during the follow-up period must be recorded with the exclusion of vitamin K antagonist. Only the type, start and stop dates, and target INR will be collected for vitamin K antagonist.
Other Medications	ACE inhibitors, inotropes, ARBs, beta blockers, antiarrhythmics, statins, nitrates, allopurinol, aldosterone blockers, antibiotics, diuretics, insulin and antidiabetic medications, and other cardiovascular medications

Clinical Investigation Plan

Study Activity	Data Collection

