2.13 Stratification by Pre-implant Aspirin Use

The primary endpoint will be analyzed by stratifying subjects that are on aspirin pre-implant of the HM3 versus subject who are not using aspirin pre-implant.

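### The primary decision rule as printed is an unadjusted risk difference; if the redacted methods do not already adjust, pre-specify a standardised risk difference over a few baseline covariates, for a modest gain in precision

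*Protocol*

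**What the plan says.** Protocol Appendix VIII (CIP Summary, Primary Endpoint Evaluation) gives the visible decision rule. Each arm's success rate is the "number of subjects who survive to 12 months with no primary endpoint events divided by the total number of subjects" in the mITT population. The test uses the "lower boundary of the one-sided 97.5% confidence limit" of the "risk difference in the composite success between treatment arms (Placebo-arm minus Aspirin-arm"), compared with a margin of 10%, which on this scale means a lower limit above -10 points. The row mentions no covariate, stratum or model.

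Protocol section 6.4, Table 3 lists what is recorded at baseline. It includes age, stroke history and "history of bleeding (diverticular disease, diagnosed arteriovenous malformations (AVMs), GI ulcer(s), anemia and/or erythropoietin treatment"). The assessment schedule in section 6.3 also has a baseline antiplatelet medication log and a baseline check for aspirin-containing products.

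The readable text uses these values in three ways:
- SAP 2.9 tabulates baseline characteristics by arm.
- Protocol 5.4.1 plans analyses by age, below 65 against 65 and over.
- SAP 2.13 says "The primary endpoint will be analyzed by stratifying subjects that are on aspirin pre-implant of the HM3", against those who are not.

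The sections that would state the estimator in full are redacted: Protocol section 8 (its contents list includes a section 8.2.2 on primary endpoint methodology) and SAP 2.3.1.2 to 2.3.1.5 and 2.7. The randomisation text, which would name any stratification factors, cannot be read either.

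**The concern.** A crude difference in proportions ignores whatever baseline variables predict about the outcome. In a non-inferiority trial the width of the interval bears directly on the decision, because a wide interval can cross the margin when the arms are truly alike. Standardising over prognostic baseline variables narrows the interval without changing the question. It also corrects for chance imbalance in the listed variables.

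The documents give reason to expect some prognostic value. Section 1.1.1 describes an HM3 series in which antithrombotic therapy was assigned by bleeding risk, and the sponsor has chosen to look at results by age and by pre-implant aspirin use. At stake is a modest amount of power for data that the trial collects anyway.

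**Working it through.** **Inputs from the documents.** Sample size: "This study will enroll enough subjects to randomize 628 subjects in the clinical investigation" (Protocol 5.7). Allocation: "Subjects will be randomized in a 1:1 ratio" (Protocol 3.0), hence 628 / 2 = 314 per arm. One-sided alpha is 0.025 and the margin is 10 points (Appendix VIII).

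**Assumed, because the documents do not give them.** The true success rate p is equal in both arms, at 50%, 60% or 70%. R² is the share of outcome variance explained by the baseline covariates, taken as 2% to 15%.

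**The planned 628.** It can be neither reproduced nor refuted, because the planning success rate, power and loss are redacted. With the usual unpooled formula, several assumed sets come close:
- 75% success, 80% power and 5% loss give 622.
- 80% success, 80% power and 20% loss give 630.
- 80% success, 85% power and 10% loss give 640.

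The power figures below are therefore illustrations, not the sponsor's own.

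**Formulas.**
- SE = sqrt(2 p (1 - p)(1 - R²) / 314)
- power = Phi(0.10 / SE - 1.96)
- equivalent crude N = 628 / (1 - R²)

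**Worked case, p = 70%.** Crude SE = sqrt(2 × 0.7 × 0.3 / 314) = 0.0366, and power = Phi(2.734 - 1.96) = 78.1%. With R² = 5%, SE = 0.0366 × sqrt(0.95) = 0.0356, and power = Phi(2.805 - 1.96) = 80.1%.

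| R² | Power, p = 50% | Power, p = 60% | Power, p = 70% | CI half-width at 60% (points) | Equivalent N |
|---|---|---|---|---|---|
| 0 (crude) | 70.7% | 72.5% | 78.1% | 7.66 | 628 |
| 2% | 71.6% | 73.4% | 78.9% | 7.59 | 641 |
| 5% | 72.9% | 74.7% | 80.1% | 7.47 | 661 |
| 10% | 75.2% | 76.9% | 82.2% | 7.27 | 698 |
| 15% | 77.6% | 79.2% | 84.3% | 7.07 | 739 |

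Across the three success rates the gain is 0.8 to 0.9 points at R² 2%, 2.0 to 2.2 at 5%, 4.1 to 4.5 at 10% and 6.2 to 6.9 at 15%.

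**Fewer analysed subjects.** Protocol 5.4 and 5.5 remove some randomised subjects for events in the first 14 days, so the mITT count will be somewhat below 314 per arm. With an assumed 10% loss (282 per arm) and 60% success, crude power is 67.9%, rising to 70.1% at R² 5%. The gain is again about 2 points.

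**Simulation check.** Logistic model, marginal standardisation, influence-function standard error, 314 per arm, 60% success and 1,500 trials per setting. One baseline score had R² of 0.021, 0.054, 0.097 and 0.145 (AUC 0.585, 0.635, 0.677 and 0.719). Adjusted-to-crude variance ratios were 0.977, 0.924, 0.906 and 0.826. Power moved from 72.8% to 73.5%, 72.1% to 73.8%, 73.7% to 77.5% and 73.1% to 79.5%. Monte Carlo error on each power figure is about sqrt(0.725 × 0.275 / 1500) = 1.2 points, which accounts for the scatter in the crude values. The mean adjusted and crude differences agreed within 0.001, so the estimand and margin keep their meaning.

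**The case against.** The strongest objection is that the visible rule is a summary row in an appendix. Protocol 4.1 sends the reader to section 8 and the SAP for details, and those details are redacted. SAP reference 3, on equivalence with censored data, is cited nowhere in the readable text, which suggests that further methods lie under the redaction. This stands. A reader might infer that the plan leaves its baseline information unused, but the documents do not support that. Redacted text is not missing text, and age and pre-implant aspirin already have planned analyses. Those analyses do not adjust the primary test, however.

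Second, a crude risk difference in a 1:1 randomised, double-blind trial is a valid estimator. That also stands: there is no bias, no inflation of type I error and no contradiction between sections.

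Third, the gain is small and assumed. No R², AUC or other measure of prognostic strength appears in the documents. Excluding patients with mandated presence or absence of antiplatelets (Protocol 5.3.2) may narrow the spread of baseline risk and lower R² further. If removing aspirin truly reduces bleeding, power starts higher and adjustment adds less.

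Fourth, a reader might take bleeding history to be the main driver of the composite. Section 1.1.1 reports a two-year bleeding rate of 43.7% in the earlier HM3 cohort. That shows bleeding events are common, not that a history of bleeding predicts them.

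These points limit the claim without removing it. The printed test is unadjusted, and the alternative keeps the same scale and margin.

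**Conclusion.** The concern holds in a conditional form. The primary rule as printed is an unadjusted risk difference, and whether the redacted methods adjust it cannot be seen. If they do not, standardisation over a few baseline covariates is worth pre-specifying.

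With 314 per arm, no true difference and 50-70% success, the likely gain is about 1 to 2 power points for R² of 2-5% and about 4 points for R² of 10%. R² and the success rates are assumptions.

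A reader might infer from the 70% case that adjustment lifts the trial past 80% power. That is not supported. The crossing depends on the chosen success rate and on counting every randomised subject: at 60% success the same R² of 5% moves power from 72.5% to 74.7%. The downside is small, with little or no gain if the covariates predict weakly.

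**What to change.** The sponsor should first confirm what SAP 2.3.1.3 and Protocol 8.2.2 specify. If adjustment is not already there, amend the SAP before unblinding as follows:

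- **Estimator.** Fit a logistic model for composite success in the mITT population with treatment, age, bleeding history, stroke history, pre-implant aspirin use and any randomisation factors. Predict each subject's success probability under placebo and under aspirin, average each over all subjects, and take the difference (g-computation).
- **Inference.** Use a robust standard error and the one-sided 97.5% lower limit, with the same -10-point limit.
- **Covariates.** Use only values measured before randomisation, with coding fixed in advance.
- **Contingencies.** State a simple rule for missing covariates that does not depend on arm, and a fallback to the crude difference if the model does not converge.
- **Sensitivity analysis.** Report the crude risk difference alongside. Keep the planned analyses by age and pre-implant aspirin use as they are.

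The cost is a further SAP revision (the current one is Version F) and some programming. It needs no new data, visits or subjects.

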1.0 SYNOPSIS OF STUDY DESIGN

1.1 Purpose of the Statistical Analysis Plan

This statistical analysis plan (SAP) is intended to provide a detailed and comprehensive description of the planned methodology and analysis to be used for CIP 10305, the ARIES HM3 clinical investigation. Version F of the SAP is based on the Version C, March 13, 2020 Clinical Investigation Plan

1.2 Clinical Investigation Objectives

To study the safety and efficacy of an anti-platelet-free antithrombotic regimen in patients with advanced heart failure treated with the HM3 LVAS

1.3 Clinical Investigation Design

This is a prospective, randomized, double-blinded, placebo-controlled clinical investigation of advanced heart failure patients treated with the HM3 with two different antithrombotic regimens: vitamin K antagonist with aspirin vs vitamin K antagonist with placebo. [REDACTED]

The clinical investigation has been designed to involve as little pain, discomfort, fear, and any other foreseeable risk as possible for subjects.

The clinical investigation will be conducted at up to 50 centers worldwide. The primary, and secondary endpoints will be evaluated as described in this SAP. Outcomes for this study include death, transplant, withdrawal or pump exchange. All subjects, site, Clinical Events Committee (CEC), and sponsor personnel, will remain blinded to the randomization scheme until the last ongoing study subject completes follow-up (specifically, experiences an outcome or reaches 12-months of follow up) and all data have been collected and adjudicated, exceptions will be justified in the study blinding plan (eg. DSMB). After a patient reaches 12-months of follow up, they will continue to be followed every 6-months, as long as they remain on the treatment arm medication, until the last ongoing patient reaches 12-months of follow up. Beginning at the 12-month follow-up visit, patients should be requisitioned two bottles of the treatment arm medication to cover the 6 months until the next follow up visit.

1.4 Endpoints

1.4.1 Primary Endpoint

The primary endpoint for this study will be met if the placebo arm is non-inferior to the aspirin arm in the composite of survival free of any non-surgical¹ major hemocompatibility related adverse event² at 1-year post implant.

¹ - Non-surgical – any event occurring > 14-days post implant.

² - Major Hemocompatibility Related Adverse Event:

- Stroke
- Pump Thrombosis (suspected or confirmed)
- Bleeding (including intracranial bleeds that do not meet the stroke definition)
- Arterial Peripheral Thromboembolism

Statistical Analysis Plan

This study assesses the overall change in the overall incidence of major hemocompatibility related adverse events. Additional secondary endpoints will also be evaluated to monitor effects on other study outcome measures.

This composite primary endpoint reflects the interrelatedness of hemocompatibility related adverse events, providing an endpoint that will result in a clear answer to the study's primary question of whether or not anti-platelets are required to maintain the safety and efficacy profile of the HM3. Because post-implant clinical course can be widely variable due to clinical responses to adverse events, this composite endpoint focuses on the first major hemocompatibility related adverse event to ensure the effect of the treatment arm is reflected in the primary endpoint measure. Non-composite endpoints or endpoints that do not focus on the first event have the possibility of being rendered futile or distorted by treatment responses to prior adverse events.

